7.8 Statistical Analysis of Primary and Secondary Effectiveness Endpoints

In testing for non-inferiority of the primary effectiveness, a two-tailed 95% confidence interval (CI) for the difference in two rates will be used to examine the location of the lower boundary of the CI relative to the 10% NI delta. An NI delta of 10% is judged to be clinically acceptable for this indication. Further, given an expected 30% advantage of the test device over the active control (80% vs 50%), by setting the non-inferiority margin at 10%, we are retaining 67% of the active treatment advantage as opposed to a using a

more standard value of 50% (Non-Inferiority Clinical Trials to Establish Effectiveness Guidance for Industry, U.S. Department of Health and Human Services Food and Drug Administration Center for Drug Evaluation and Research (CDER) Center for Biologics Evaluation and Research (CBER) November 2016 Clinical/Medical).

In testing for superiority of the primary effectiveness endpoint, the same logistic regression model, used to test for NI will be evaluated. Alpha of 0.05 will be used to test for significance.

The secondary effectiveness endpoint will be tested with a Wilcoxon rank-sum test. An alpha of 0.05 will be used to test for significance.

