7.3 Sample Size

Assuming a response rate for Barrett's esophagus with EndoRotor® ablative therapy of 80%, and for cryoablation of 50%, the study will have over 95% power to demonstrate non-inferiority (NI), given a NI delta of 10%, of EndoRotor® to cryoablation and will have 91.6% power to demonstrate superiority of EndoRotor® over continued ablative therapy using a sample size of 110 evaluable subjects, 55 in each treatment group.

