7.6 Effectiveness Hypotheses

Primary Endpoint Hypothesis 1 (non-inferiority): It is hypothesized that EndoRotor® will not have fewer subjects with complete removal than those treated with control.

$$\begin{array}{ll} \text{Null Hypothesis:} & nE - \delta \leq nC \\ \text{Alternate Hypothesis:} & nE - \delta > nC \end{array}$$

Where nE =Proportion with successful treatment in EndoRotor® arm; nC = proportion with successful treatment in the control arm and δ is a non-inferiority margin of 10% (which is subtracted from nE).

Primary Endpoint Hypothesis 2 (superiority): The proportion of subjects with successful eradication areas of Barrett's metaplasia will be greater for those treated with EndoRotor® than for those treated with control.

$$\begin{aligned} \text{Null Hypothesis: } & nE \leq nC \\ \text{Alternate Hypothesis: } & nE > nC \end{aligned}$$

Where nE =Proportion with successful treatment in EndoRotor® arm; nC = proportion with successful treatment in the control arm.

Secondary Endpoint Hypothesis: The percentage tissue removal of Barrett's metaplasia will be greater for those treated with EndoRotor® than for those treated with control.

$$\begin{aligned} \text{Null Hypothesis: } & \mu E \leq \mu C \\ \text{Alternate Hypothesis: } & \mu E > \mu C \end{aligned}$$

Where μE =mean % tissue removal for EndoRotor® arm; μC = mean % tissue removal for control arm.

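### The 67% retention figure offered for the 10-point non-inferiority margin is computed on EndoRotor's expected gain over control, so it is not a share of the control's own effect

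*Combined protocol and SAP*

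**What the plan says.** Section 7.8 gives two reasons for the margin. The first is clinical: "An NI delta of 10% is judged to be clinically acceptable for this indication". The second is quantitative. It begins "given an expected 30% advantage of the test device over the active control (80% vs 50"%) and concludes that a 10% margin means "retaining 67% of the active treatment advantage", which it contrasts with a "more standard value of 50"% and supports with a citation to a regulatory guidance on non-inferiority trials.

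The same two rates are the planning assumptions in section 7.3: "Assuming a response rate for Barrett's esophagus with EndoRotor® ablative therapy of 80%, and for cryoablation of 50"%. Under 7.8, non-inferiority is judged by where the lower limit of a two-sided 95% confidence interval for the difference in rates falls relative to the 10% delta. Under 7.8.3, non-inferiority is the first test in the sequence. If it fails, testing stops; if it succeeds, superiority is tested, and then the secondary endpoint.

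**The concern.** A non-inferiority margin limits how much of the active control's benefit a new treatment may give up. A statement that a given share is retained therefore needs an estimate of that benefit, meaning control compared with no treatment. The 30 points in 7.8 are a different quantity: how much better than control the sponsor expects EndoRotor to be. That expectation carries no information about how much of the control's effect could be lost.

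The margin is the decision threshold for the first test, and the 67% is its only quantitative support. Because the figure is set against a supposedly standard 50% and carries a guidance citation, a reader would take it that a preserved-effect calculation had been made and had come out stricter than usual. If the trial met non-inferiority but not superiority, the margin would carry the whole effectiveness claim, and the report could repeat a retention figure that the design does not deliver.

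**Working it through.** **Inputs from the documents.** Margin 10 points (7.6, 7.8). Expected response 80% for EndoRotor and 50% for control (7.3, 7.8). Evaluable subjects 55 per arm (7.3). Two-sided 95% interval (7.8). Stated retention 67% (7.8).

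**1. Reproduce the 67%.** Retention = 1 − margin/base. With the base at 80 − 50 = 30 points, 1 − 10/30 = 66.7%. The plan's figure is reproduced, and the base is EndoRotor minus control, as 7.8 itself says.

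**2. See how the figure behaves.** Keep the margin at 10 points and raise the expected gain to 40: 1 − 10/40 = 75%. Alternatively, keep the gain at 30 and apply the 50% standard: the allowed margin is 0.5 × 30 = 15 points. On this logic, a more hopeful view of the device makes the same margin look stricter, or permits a wider one.

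**3. Compare it with what the test secures.**
- Confidence-interval rule in 7.8, read conventionally: at the boundary EndoRotor minus control is −10 points. As a share of the expected gain, −10/30 = −33%.
- Hypothesis as literally written in 7.6, where "δ is a non-inferiority margin of 10% (which is subtracted from nE"): the alternative is that EndoRotor minus 10 points exceeds control. The boundary is then +10 points, or 10/30 = 33%.

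Neither boundary gives 67%.

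**4. Try the right base.** Retention = 1 − 10/(control effect over no treatment). The documents do not give that effect. Section 1.3 reports only single-group responses: 80% of 46 refractory patients, after a median of 24 months of various therapies, and 55% in a mixed primary and rescue cryotherapy cohort of 64 at 12 months. The control effects below are therefore assumptions.

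| Assumed control effect (points) | Share retained with a 10-point margin |
|---|---|
| 5 | −100% |
| 10 | 0% |
| 15 | 33% |
| 20 | 50% |
| 30 | 67% |
| 40 | 75% |
| 50 | 80% |

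The last row corresponds to a control response of 50% and an untreated response of 0%. Half the control effect is kept only if that effect is at least 20 points. The stated 67% would be right only if it happened to be 30.

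**5. Check what is not affected.** The standard error is √(0.8 × 0.2/55 + 0.5 × 0.5/55) = 0.0863.
- Non-inferiority power: (0.30 + 0.10)/0.0863 − 1.96 = 2.67, giving 99.6%. This agrees with "over 95% power to demonstrate non-inferiority (NI), given a NI delta of 10"%.
- Superiority power: the pooled two-proportion formula gives 92.1%, close to the plan's statement that the study "will have 91.6% power to demonstrate superiority of EndoRotor® over continued ablative therapy".

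Neither calculation uses the 67%. Under the planning rates, the chance of meeting non-inferiority but not superiority is about 99.6 − 92.1 = 7.5%.

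**The case against.** The best defence is that little depends on this sentence. The clinical-acceptability statement comes first and stands by itself, and the 67% is added as a further argument. Deleting it changes no margin, sample size, test, significance level or testing order. Under the planning rates the margin alone decides the outcome in only about 7.5% of trials, because a lower limit above zero also lies above −10. This stands, and it keeps the point at the level of a rationale to be corrected. It does not rescue the figure: the clinical statement comes with no data, so the 67% is all the numerical support there is. The 7.5% would also be larger if the planning rates proved somewhat optimistic.

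Three stronger readings are tempting, and the documents do not support them.
- A reader might infer that 10 points is too wide. That needs the control's effect over no treatment, which is not given.
- A reader might infer the reverse. With control at 50% and untreated response at 0–10%, the control effect is 40–50 points and the margin retains 75–80%, more than the plan claims. That untreated rate is an assumption, and it shows only the favourable end of the range.
- A reader might infer that a device at the margin always keeps none of the expected gain. This holds under the interval rule in 7.8. The hypothesis as written in 7.6 puts the boundary at +10 points, or 33%. That conflict between 7.6 and 7.8 is a separate matter and needs its own correction.

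**Conclusion.** The point holds as a misstated justification. The 67% is correct arithmetic on the wrong base. It is not a share of the active control's effect, it moves with optimism about EndoRotor, and it is not secured at the boundary of the 7.8 interval rule, where EndoRotor is 10 points worse than control. The share actually retained cannot be computed from the documents. Over assumed control effects of 10 to 50 points it runs from 0% to 80%.

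The consequence is limited to what may be claimed from a result that meets non-inferiority only. Taking the 7.8 interval rule as the operative test, a superiority conclusion does not depend on the margin. Whether 10 points is an acceptable margin remains open.

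**What to change.** In section 7.8, delete the sentence containing the 67% and its comparison with 50%, and let the margin rest on the clinical judgement already stated there. Add that a non-inferiority result will not be described as preserving any share of the control's effect unless a sourced estimate of control against no treatment, on this trial's endpoint, is supplied and the share is restated on that base. Make the change before outcome results are known.

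The deletion costs a wording amendment and leaves the margin, sample size, tests and testing sequence as they are. Its downside is that the written case for the margin becomes less favourable. The optional estimate is more than wording: the documents contain no untreated comparator, so evidence would have to be found. If the margin were then derived from that evidence, it might not come out at 10 points.

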7.0 STATISTICAL METHODS

7.1 General Principles

By-subject listings will be created for each CRF module. Summary tables for continuous variables will contain the following statistics: N, mean, median, standard deviation, minimum, maximum, and 95% confidence interval (CI) as appropriate. Summary tables for categorical variables will include N, percentage, and 95% CIs on the percentage. CIs for proportions will be calculated using the Clopper- Pearson exact method. Graphical techniques will be used when such methods are appropriate and informative. Tables will separate data by treatment arm.

Transformations of the data may be explored if warranted by the distribution of the data. Analyses resulting from transformations applied after the data are unmasked will be considered to be exploratory.

Unless otherwise specified, all analyses will be 2-sided at the 0.05 level of significance. All analyses will be performed using SAS® (Version 9.4) and graphs using R, version 3.3.1 or later, or using SAS®.

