7.4 Statistical Analysis

The Primary effectiveness endpoint will be compared across treatment arms using a logistic regression, where the predictor variable is treatment arm with EndoRotor® coded 1 vs 0 for cryotherapy or ablative therapy (i.e., control). Covariates included in the model will be: subject's age, dysplasia (low-grade or high-grade), length of Barrett's lesion in cm, and duration of disease (months). The lower boundary of the predicted proportion

difference will be used to compare the two arms for the non-inferiority test and for the subsequent superiority test. In the event that missing data are present in the ITT analysis population, then multiple imputation will be performed with SAS procedures MIIMPUTE and MIANALYZE, as described in section 7.5.

The secondary endpoint, percentage reduction, will be compared using a Wilcoxon rank-sum test. In the event of missing data, The ITT analysis will be performed with data imputed by multiple imputation.

In the event of missing data, sensitivity analyses will be performed for the ITT analysis population using best case and worst case analyses as described below. Discrepant findings will be followed by tipping point analyses.

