7.5 Missing Data

1. If there are missing primary endpoint data, then ten imputations of missing binary primary endpoint will be produced using SAS PROC MI using the Markov chain Monte Carlo algorithm. The seed used to begin random number generation will be 20170623. The following variables will be used as predictors: site, subject's age, dysplasia (low-grade or high-grade), length of Barrett's lesion in cm, and duration of disease (months). Analysis with SAS PROC MIANALYZE will follow.
2. For the secondary endpoint, percentage reduction, ten imputations will be produced for the randomized cohort using SAS PROC MI. The seed used to begin random number generation will be 20170623. The Markov chain Monte Carlo method will be used to compute full imputations using the following variables: site, subject's age, dysplasia (low-grade or high-grade), length of Barrett's lesion in cm, and duration of disease (months). Analysis with SAS PROC MIANALYZE will follow.

The following secondary analyses will be performed to assess the sensitivity of the results to missing data for the primary effectiveness endpoint.

- The best-case scenario will assume success for all missing data treated with EndoRotor and failure for all missing data treated with control.
- The worst-case scenario will assume failure for all missing data treated with EndoRotor and success for all missing data treated with control.
- If the best and worst case analyses lead to different statistical conclusions, then a tipping point analysis will report the proportion of successes or failures for each arm at point the statistical conclusion would change.

A similar approach will be used for the continuous percentage secondary endpoint. Best case will assume 100% removal for EndoRotor® and 0% for control; worst case will assume 0% removal for EndoRotor® and 100% for control; If the results differ using the two imputation rules, then the imputed values will be incremented on 1% values until the point where the conclusion changes is identified.

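### The secondary endpoint is tested without the covariates already planned for the primary model, and no estimate and standard error are named for pooling over imputations; a covariate-adjusted rank analysis would settle both, with a small and conditional power gain

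*Combined protocol and SAP*

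**What the plan says.** - **Test.** Section 7.4: "The secondary endpoint, percentage reduction, will be compared using a Wilcoxon rank-sum test". Section 7.8 repeats this: "The secondary effectiveness endpoint will be tested with a Wilcoxon rank-sum test". It adds: "An alpha of 0.05 will be used to test for significance". Section 7.1 makes it two-sided: "Unless otherwise specified, all analyses will be 2-sided at the 0.05 level of significance".
- **Covariates.** In 7.4 these belong to the primary logistic model only: "Covariates included in the model will be: subject's age, dysplasia (low-grade or high-grade), length of Barrett's lesion in cm, and duration of disease (months").
- **Missing data.** Section 7.5, item 2: "For the secondary endpoint, percentage reduction, ten imputations will be produced for the randomized cohort using SAS PROC MI". The imputation variables are site and the same four covariates. The item ends: "Analysis with SAS PROC MIANALYZE will follow". The quantity to be pooled is not named.
- **Hypothesis.** Section 7.6 states the secondary hypothesis as a difference in mean percentage removed.
- **Sequence.** Under 7.8.3 the secondary endpoint is tested only after primary superiority has been shown. It is the only secondary endpoint in that sequence.

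**The concern.** The plan uses four baseline variables to adjust the primary comparison and to predict missing values of percentage reduction, then leaves them out of the test of percentage reduction. No reason is given. If the variables predict the outcome, some power that costs nothing to collect goes unused.

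The missing-data route is also incomplete. MIANALYZE combines an estimate and its standard error from each imputed data set. The primary logistic model supplies both. For the secondary endpoint the plan specifies only a rank-sum test and no accompanying estimate, so someone must choose one later, possibly after seeing data. Section 4.5 allows for 10 of 120 subjects lost to follow-up (8.3%), so the imputed ITT analysis will probably be needed.

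**Working it through.** **1. The plan's own power figure.** Section 7.3 gives 91.6% for primary superiority at 80% vs 50%, 55 per arm. With a pooled-variance test:

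z = [0.30 − 1.96·√(2·0.65·0.35/55)] / √((0.8·0.2 + 0.5·0.5)/55) = (0.30 − 0.1783)/0.0863 = 1.41, so power = 92.1%.

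This agrees to within a point. The documents state no effect size, SD, R² or power for the secondary endpoint, so what follows rests on assumptions.

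**2. Shape of the endpoint.** A subject with complete removal has 100% reduction. At the plan's rates, about 80% and 50% of the arms would sit at that single value. The comparison therefore has to be made with a spike at 100%.

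**3. Simulation with one covariate.** There were 4,000 trials per setting with 55 per arm. Responders were set at 100% and non-responders drawn from Beta(2,2) (assumed). One normal covariate was correlated 0, 0.3 or 0.5 with the latent outcome. R² is the squared correlation with percentage reduction in the control arm. Tests are two-sided at 0.05.

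| Cleared | R² | Wilcoxon | Rank ANCOVA | Difference | ANCOVA on raw % | Difference |
|---|---|---|---|---|---|---|
| 80% vs 50% | 0.02 (chance) | 90.9 | 90.8 | −0.1 | 84.2 | −6.7 |
| 80% vs 50% | 0.09 | 90.4 | 92.0 | +1.6 | 85.8 | −4.6 |
| 80% vs 50% | 0.21 | 90.5 | 94.7 | +4.2 | 89.5 | −1.0 |
| 70% vs 50% | 0.02 (chance) | 54.3 | 54.3 | 0.0 | 45.7 | −8.6 |
| 70% vs 50% | 0.09 | 53.2 | 55.2 | +2.0 | 47.9 | −5.3 |
| 70% vs 50% | 0.21 | 53.2 | 61.8 | +8.6 | 53.0 | −0.2 |

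Monte Carlo standard error: √(0.9·0.1/4000) = 0.5 points near 90%, and √(0.54·0.46/4000) = 0.8 points near 54%. With no treatment effect, rejection was 4.8% and 5.6% for Wilcoxon and 4.7% and 5.2% for rank ANCOVA (correlation 0 and 0.5).

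**4. Four covariates, as the plan would fit.** Each extra covariate uses a degree of freedom, so a single ideal covariate flatters the adjustment slightly. With four fitted:

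- 80% vs 50%: gain of about 2 to 4 points when they explain about 13 to 20% of rank variance.
- 70% vs 50%: Wilcoxon about 53 to 55%, gain of about 4 to 7 points.
- Covariates unrelated to outcome: loss of about 1 to 2 points.
- Type I error 4.6 to 5.3%.

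**5. Allowing for the testing sequence.** What matters is the chance of passing primary superiority and then the secondary test. At 80% vs 50%, with a covariate-adjusted primary test, this is 89 to 90% with Wilcoxon and 89 to 94% with rank ANCOVA: gains of 0, 2 and 4 points for a covariate with log-odds SD 0, 0.7 and 1.0.

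**6. Pooling.** Sections 7.4, 7.5 and 7.8 together contain no location-shift estimate, no Mann-Whitney probability with a standard error, and no rule for combining ten rank-sum results.

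**The case against.** The rank-sum test is a defensible, prespecified choice for a bounded endpoint with many ties. Step 3 shows that ordinary ANCOVA on the raw percentages does worse, by up to about 9 points. That stands, and it rules out one obvious replacement.

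Prognostic strength is not documented. Section 7.4 lists the covariates without giving an R², and section 5.6 already uses prior length as the denominator of the endpoint, so what length still predicts is unknown. That also stands.

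Two stronger readings are tempting. A reader might infer that the Wilcoxon test definitely loses power, or loses a great deal. For a normal endpoint with standardized difference 0.5 and 55 per arm, the usual formulas give 72.7% for Wilcoxon and 88.0% for ANCOVA at R² = 0.30, a difference of about 15 points. The documents support neither that R² nor normality, and with uninformative covariates the adjustment costs a little. A reader might also infer that a rank-sum analysis cannot be pooled. It can: a Hodges-Lehmann shift or a Mann-Whitney probability, each with its standard error, would serve. The gap is that none is named. One added sentence would close it with the Wilcoxon test kept, and it matters only if secondary data are missing.

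**Conclusion.** The point holds as an inexpensive improvement to the secondary analysis. Two facts are plain in the text: the test ignores four covariates that are planned for the primary model and for imputing this endpoint, and the quantity to be pooled is unspecified.

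The power benefit is modest and conditional: about 2 to 4 points at the design rates, 4 to 7 if the control does as planned but only 70% clear with EndoRotor, and a loss of 1 to 2 if the covariates carry no information. These figures assume 55 per arm, full clearance scored as 100%, a Beta(2,2) distribution for the rest, and covariates explaining about 13 to 20% of rank variance. The primary analysis and its power are untouched, and the secondary test is reached only after primary superiority.

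**What to change.** In 7.4 and 7.8, make the secondary test a covariate-adjusted rank analysis with treatment arm and the four covariates of the primary model. Either a rank ANCOVA or a proportional-odds model would do; choose one in advance.

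In 7.5, item 2, name what is pooled. For rank ANCOVA, rank within each imputed data set and pass the treatment coefficient and its standard error to MIANALYZE. For proportional odds, pass the log odds ratio and its standard error.

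Keep the plain Wilcoxon as a sensitivity analysis. Do not substitute ordinary ANCOVA on the raw percentages.

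In 7.6, restate the secondary hypothesis to match the chosen estimate. Neither the present Wilcoxon test nor its adjusted counterparts estimate a difference in means.

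The cost is SAP wording and a little programming. No new data are needed, since all four covariates are already planned for.

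### The secondary hypothesis is stated in means but tested only by Wilcoxon rank-sum, which does not test means here and names nothing for PROC MIANALYZE to pool

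*Combined protocol and SAP*

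**What the plan says.** Section 7.6 writes the secondary null as μE ≤ μC and the alternative as μE > μC. It defines the two parameters as "mean % tissue removal for EndoRotor® arm" and "mean % tissue removal for control arm".

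The only test named is a rank test. Section 7.4: "The secondary endpoint, percentage reduction, will be compared using a Wilcoxon rank-sum test". Section 7.8: "The secondary effectiveness endpoint will be tested with a Wilcoxon rank-sum test", followed by "An alpha of 0.05 will be used to test for significance". Under Section 7.1, unless otherwise specified, "all analyses will be 2-sided at the 0.05 level of significance".

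For missing secondary data, Section 7.5 (item 2) calls for ten imputations, and then "Analysis with SAS PROC MIANALYZE will follow". No effect measure for the secondary endpoint is named in Sections 7.4, 7.5 or 7.8.

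Section 7.8.3 allows the secondary test only after superiority on the primary endpoint.

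**The concern.** The rank-sum test asks whether a value from one arm tends to exceed a value from the other. That matches a comparison of means when the arms differ by something like a shift of one distribution shape. A percentage with a ceiling at 100%, and different shares of each arm at that ceiling, is not a shift. The plan neither assumes a shift, nor adds a mean-based test, nor requires the means to agree in direction.

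Two things are at stake. First, the planned test does not control error for the null hypothesis as written, so a significant result would not establish the stated alternative. Second, the imputed ITT analysis cannot be run as described: MIANALYZE combines a point estimate and its standard error across imputations, and a rank-sum p-value provides neither.

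**Working it through.** **Inputs from the plan (Section 7.3).** Response 80% against 50%, 55 evaluable per arm. No power figure is given for the secondary endpoint. The primary superiority figure is 91.6%. As a check on the inputs, with a pooled null variance:
- SE under the null = √(0.65 × 0.35 × 2/55) = 0.0910
- SE under the alternative = √((0.16 + 0.25)/55) = 0.0863
- power = Φ((0.30 − 1.96 × 0.0910)/0.0863) ≈ 92.1%, close to the stated 91.6%.

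**Assumed.**
- Every complete responder has 100% removal.
- Non-responders in each arm share one fixed value, e for EndoRotor and c for control, varied below. The documents give no partial-removal figures.
- The percentage is read as removal, as in Section 7.5. The formula in Section 5.6 (follow-up length over prior length), taken literally, gives the residual fraction, so the direction has to be fixed before any test.

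**Counts.** EndoRotor 0.80 × 55 = 44 at 100% and 11 at e. Control 0.50 × 55 = 27.5, taken as 28 at 100% and 27 at c. At the ceiling: 72 of 110 values, or 65%.

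**Rank test when e < c.**
- U = 0.5 × 44 × 28 + 44 × 27 + 0 = 616 + 1188 = 1804
- U/(55 × 55) = 1804/3025 = 0.596, which is P(E > C) + 0.5 P(tie)
- expected U under the null = 3025/2 = 1512.5
- tie term: Σ(t³ − t) = 373176 + 19656 + 1320 = 394152 for tie groups of 72, 27 and 11
- variance = (3025/12) × (111 − 394152/(110 × 109)) = 252.08 × 78.13, so SD = 140.3
- z with continuity correction = (1804 − 1512.5 − 0.5)/140.3 = 2.07, two-sided p = 0.038

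U and p do not depend on e and c as long as e < c < 100.

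**Means.** EndoRotor = (4400 + 11e)/55; control = (2800 + 27c)/55.

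| Non-responders, E vs C (assumed) | Mean E | Mean C | Wilcoxon p (favours E) | Welch p |
|---|---|---|---|---|
| 20% vs 80% | 84.0 | 90.2 | 0.038 | 0.18 |
| 20% vs 67% | 84.0 | 83.8 | 0.038 | 0.97 |
| 20% vs 50% | 84.0 | 75.5 | 0.038 | 0.13 |
| 50% vs 50% | 90.0 | 75.5 | 0.0014 | 0.0012 |

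For the last row the non-responders tie: U = 616 + 1188 + 0.5 × 11 × 27 = 1952.5, with tie groups of 72 and 38, SD = 137.8 and z = (440 − 0.5)/137.8 = 3.19.

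**When the means reverse.** Setting the means equal gives c = (1600 + 11e)/27. The control non-responders must exceed about 59% if e = 0, 67% if e = 20, and 80% if e = 50.

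**Error rate for the stated null.** In simulations of 5,000 trials per scenario, non-responders had beta-distributed removal (a fixed 0% for EndoRotor in the 80% scenario) and true means were equal at 80, 84 or 88%. Wilcoxon favoured EndoRotor in 56–61% of trials, against a nominal 2.5% in that direction. Welch did so in 3.5–4.2%. Every one of these significant Wilcoxon results also passed the primary-superiority gate (applied as an unadjusted chi-square), because the excess of complete responders that opens the gate also drives the rank test.

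**The case against.** The strongest reply is that the reversal rests on values found nowhere in the plan. That stands. It needs EndoRotor non-responders to have clearly less removal than control non-responders; with equal partial removal the two tests agree. Even in the 20% against 80% example the mean deficit is not itself significant (Welch p=0.18). The 100% point mass is also an assumption. Section 5.8.1 limits EndoRotor treatment to 270 degrees and acts on biopsies in the treated segment, while Section 5.6 measures the secondary endpoint by overall length. Some EndoRotor responders could therefore fall below 100%, which would change the ties.

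Three stronger readings are tempting, and the documents do not support them.
- **That the rank test ignores non-responders.** It ranks them. With 44 and 28 complete, p is 0.038 if EndoRotor non-responders are the worse group, 0.0014 if they tie, and 0.00003 if they are the better group (80% against 20%). It uses their order but not how much disease remains.
- **That a significant result would be reported as greater mean removal.** No section prescribes that wording. The verbal hypothesis in Section 7.6 speaks only of greater percentage removal, and Section 7.1 puts means in the summary tables by arm, so a lower EndoRotor mean would be visible.
- **That Wilcoxon is a wrong choice for a bounded percentage.** It is a common one. The fault lies in pairing it with a hypothesis about means.

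It is also fair to say that the MIANALYZE gap arises only if secondary data are missing, and that the per-protocol analysis (Section 7.2) does not impute.

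**Conclusion.** The point holds in a limited form. The formal secondary hypothesis and its only test address different quantities, and the plan states no condition that would make them the same. At the plan's own response rates and sample size, a significant rank test for EndoRotor is compatible with a mean 6.2 points lower (84.0 against 90.2), with means about equal, or with a mean 8.5 to 14.5 points higher, depending on partial-removal values that the documents do not give. A reversal is possible; how likely it is cannot be judged from the plan. If complete responders sit at 100%, the result is driven mainly by the complete-response share, which is already the primary endpoint.

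Separately, and without any of these assumptions, the imputed analysis lacks a named estimate and standard error to pool. Both defects are confined to one secondary claim behind a gate. Non-inferiority and superiority on the primary endpoint are unaffected.

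**What to change.** Align the hypothesis and the test before the data are unmasked.

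1. Restate the secondary hypothesis in Section 7.6 as P(EndoRotor > control) + 0.5 P(tie) > 0.5, and keep the rank comparison.
2. Report that estimate with its 95% CI, and pool the estimate and its SE over the ten imputations in MIANALYZE.
3. Report the mean difference with a bootstrap CI as descriptive, and state that greater mean removal will not be claimed from the rank test.

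This does not stop the rank result and the means from pointing in different directions. It makes the claim match the test and puts any disagreement in view. If the sponsor wants a claim about means, it should instead keep Section 7.6 and replace the rank test with a mean-based one (for example Welch or bootstrap), pooled in the same way.

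The cost is SAP wording and a few lines of code. The downside of the first option is a less familiar effect measure.
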